2.3.3. Pharmacokinetics and Pharmacodynamics

The pharmacokinetics and pharmacodynamics of belantamab mafodotin (antibody-drug conjugate, including complex) with CCI), total monoclonal antibody (total mAb; including complex), and cys-mcMMAF were investigated in 291 participants with RRMM following IV administration at doses from 0.03 to 4.6 mg/kg Q3W in Study BMA117159 (n=73) and at doses of 2.5 or 3.4 mg/kg Q3W in Study 205678 (n=218).

Maximum concentrations (Cmax) of belantamab mafodotin and total monoclonal antibody were observed at or shortly after the end of infusion (EOI), while cys-mcMMAF Cmax values were generally observed on Day 2. On a molar basis, plasma concentrations of cys-mcMMAF were <1% of belantamab mafodotin concentrations. There was limited accumulation (less than 2-fold) of belantamab mafodotin or cys-mcMMAF during subsequent cycles.

Belantamab mafodotin pharmacokinetics were well described by a linear, two-compartment population model, with a time-varying decrease in clearance in a population

pharmacokinetic analysis. At Cycle 1, belantamab mafodotin had a systemic clearance of 0.92 L/day, steady-state volume of distribution of 11 L, and an elimination half-life of 12 days in participants with RRMM in Study 205678. Over time, clearance was reduced by 28%, resulting in an elimination half-life of 14 days. The time to 50% change in clearance was approximately 50 days.

No clinically significant differences in the pharmacokinetics of belantamab mafodotin or cys-mcMMAF were observed based on age (34 to 89 years), sex, race (African American/Black and White), body weight (42 to 130 kg), mild or moderate renal impairment (eGFR \geq 30 ml/min/1.73m²) or mild hepatic impairment (NCI-ODWG classification). Higher serum levels of β_2 -microglobulin, IgG, and column and lower levels of albumin are associated with more advanced multiple myeloma or a higher multiple myeloma disease burden. Higher baseline IgG and levels, and lower baseline albumin levels were associated with higher belantamab mafodotin clearance leading to lower average and trough concentrations (Ctau) of belantamab mafodotin. Higher baseline IgG and levels were associated with higher cys-mcMMAF central volume of distribution leading to lower cys-mcMMAF Cmax.

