In nonclinical studies, cys-mcMMAF had limited metabolic clearance. *In vitro* data suggested that belantamab mafodotin and cys-mcMMAF are unlikely to perpetrate a drug-drug interaction or to be a victim of a drug-drug interaction with inhibitors or inducers of cytochromes (CYP) P450. Cys-mcMMAF was an *in vitro* substrate of organic anion transporting polypeptides (OATP)1B1 and OATP1B3, multidrug resistance associated proteins (MRP)1, MRP2, and MRP3, a borderline substrate of bile salt export pump (BSEP), and a possible substrate of P-glycoprotein (P-gp). Following the administration of belantamab mafodotin to participants with RRMM, only intact cys-mcMMAF was detected in pooled human urine, with no evidence of other MMAF-related urinary metabolites.

Free CCI levels were measured in Study BMA117159 and Study 205678. All participants exhibited reductions in free CCI concentration at end of infusion compared to baseline at Cycle 1, with a return to near-baseline level by 7 days after dosing, reflecting binding of belantamab mafodotin to CCI Maximum decreases ranged from 2% to 97%, which were qualitatively dose-dependent, with larger reductions in free CCI at higher doses.

Exposure-response analyses performed for Study 205678 and/or Study BMA117159 found that ocular safety endpoints were most strongly associated with belantamab mafodotin exposure, while efficacy endpoints had a weaker association with belantamab mafodotin exposure. Both safety and efficacy endpoints were associated with patient characteristics. Belantamab mafodotin Ctau was associated with probability of corneal events and keratopathy and cys-mcMMAF Cmax was associated with probability of thrombocytopenia. Probability of occurrence of dry eye, blurred vision, neutropenia and infusion related reaction were not associated with an exposure measure. In addition, the results of the analysis of concentration against corrected QT interval (QTc) demonstrated that belantamab mafodotin or cys-mcMMAF did not have a significant effect on cardiac repolarization.

Details of the characteristics of belantamab mafodotin, nonclinical, and clinical activity are provided in the Investigator's Brochure (IB) [Belantamab mafodotin GlaxoSmithKline Document Number RPS-CLIN-004867, 2021].

This is the first study for belantamab mafodotin in China to assess the safety, tolerability, pharmacokinetics (PK), immunogenicity and clinical activity of belantamab mafodotin in Chinese participants with MM.

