10.3.1.2. Pharmacokinetic Parameters

To assess the extent of accumulation following belantamab mafodotin repeat dosing, the observed accumulation ratio (Ro) for belantamab mafodotin, total antibody, and cys-mcMMAF will be determined as ratio of CEOI and Ctrough at Cycle 4 to CEOI and Ctrough at Cycle 1, respectively, using the data collected under Protocol 208465/Amendment 3.

Previous studies indicate that the pharmacokinetics for the third consecutive dose given at the planned interval will be at steady state. Therefore, based on the planned sampling scheme, accumulation ratios will be derived using the CEOI at Cycle 4 for Ro(CEOI) and Ctrough at Cycle 3 (predose at C4D1) for Ro(Ctrough). Participants must receive the same dose without delay or change for the first three cycles to derive Ro(Ctrough) and for the first four cycles to derive Ro(CEOI) (i.e., with dosing delays of ≤ 3 days).

$Ro(CEOI) = CEOI \text{ at C4D1} / CEOI \text{ at C1D1};$

$Ro(Ctrough) = \text{Cycle 3 trough} / \text{Cycle 1 trough}$

Accumulation ratios of CEOI and Ctrough, and other Pharmacokinetic Parameters in [Table 2](#) will be summarised using descriptive statistics for belantamab mafodotin (ADC, total antibody and cys-mcMMAF) by planned initial dose level, graphically presented (where appropriate) and listed.

CCI

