14.5.3. Reporting Standards for Pharmacokinetic

Pharmacokinetic Concentration Data	
PC Windows Non-Linear (WNL) File	PC WNL file (CSV format) for the non compartmental analysis by Clinical Pharmacology Modelling and Simulation function will be created according to Standards for the Transfer and Reporting of PK Data document. Note: Concentration values will be imputed as per GUI_51487
Descriptive Summary Statistics, Graphical Displays and Listings	
Refer to the GSK Standard PK Display Standard.
 
Refer to the GSK Standard Statistical Display Principle 6.06.1.
 
Note: Concentration values will be imputed as per GUI_51487 for descriptive summary statistics/analysis and summarized graphical displays only.

NONMEM/Pop PK File	Not applicable.
NONMEM/PK/PD File	Not applicable.
Pharmacokinetic Parameter Derivation	
PK Parameter to be Derived by Programmer	
The following PK parameter will be derived by the Programmer:
 
 Accumulation ratios based on Cycle 1 and Cycle 4 CEOI and Ctrough values
Pharmacokinetic Parameter Data	
Is NQ impacted PK Parameters Rule Being Followed	Yes, refer to [Standards for Handling NQ Impacted PK Parameters].
Descriptive Summary Statistics, Graphical Displays and Listings	Refer to GSK Standard PK Display Standard.

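### SAP 10.3.1.2 takes the third dose as steady state, but the protocol's falling ADC clearance puts the Cycle 3 trough at roughly 67–85% of it; two SAP lines also name an unsampled Cycle 4 trough

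*SAP*

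**What the plan says.** **Steady-state premise.** SAP 10.3.1.2 states "Previous studies indicate that the pharmacokinetics for the third consecutive dose given at the planned interval will be at steady state". On that basis it takes the accumulation ratios from Cycle 4 for end-of-infusion concentration (CEOI) and from Cycle 3 for trough. The displayed equations are CEOI at C4D1 over CEOI at C1D1, and Cycle 3 trough over Cycle 1 trough. The Cycle 3 trough is identified as the pre-dose sample at C4D1. Participants qualify only if the dose is unchanged and delays do not exceed 3 days. The SAP calls the ratio (Ro) an observed one and summarises it descriptively for ADC, total antibody and cys-mcMMAF.

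**Protocol PK.** Protocol 2.3.3 gives, for ADC at Cycle 1, a "systemic clearance of 0.92 L/day, steady-state volume of distribution of 11 L, and an elimination half-life of 12 days". It continues: "Over time, clearance was reduced by 28%, resulting in an elimination half-life of 14 days". Then: "The time to 50% change in clearance was approximately 50 days". It also reports accumulation of less than twofold, without naming the measure.

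**Which trough.** The first paragraph of SAP 10.3.1.2 describes both ratios as Cycle 4 over Cycle 1. SAP 14.5.3, under parameters for the programmer to derive, says: "Accumulation ratios based on Cycle 1 and Cycle 4 CEOI and Ctrough values".

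**The concern.** The SAP sentence and the protocol's PK description pull in different directions. If clearance keeps falling past the third dose, trough keeps rising, and a ratio taken at the third dose is not a steady-state ratio.

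Trough is the measure of interest for safety. Protocol 2.3.3 says "Belantamab mafodotin Ctau was associated with probability of corneal events and keratopathy", and treatment continues until progression or unacceptable toxicity. A reader who takes Ro(Ctrough) as the long-term level would place ADC exposure in Chinese participants too low.

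The second issue is one of specification. Someone programming from 14.5.3 alone would look for a trough that is never collected.

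**Working it through.** **1. The SAP statement under constant clearance.** After three doses every 21 days, the fraction of steady state is 1 − 2^(−63/t½).
- t½ = 12 days: 1 − 2^(−5.25) = 97.4%. Equivalently, with r = 2^(−21/12) = 0.297, the Cycle 3/Cycle 1 ratio is 1 + r + r² = 1.386, against 1/(1 − r) = 1.423 eventually.
- t½ = 14 days: 1 − 2^(−4.5) = 95.6%.

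So the sentence is fair if clearance is constant.

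**2. How much of the clearance fall has happened.** Pre-dose C4D1 is 3 × 21 = 63 days after the first dose. The form assumed is CL(t) = CL₀ × [1 − E × t^g / (50^g + t^g)], where E is the total fractional fall. The shape g is not in the documents, so 1, 2 and 4 were tried. The share of the fall completed at day 63 is 63^g / (50^g + 63^g) = 56%, 61% and 72%.

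**3. Cycle 3 trough with falling clearance.** From Protocol 2.3.3: CL 0.92 L/day, Vss 11 L, half-life 12 days at first and 14 days late, CL −28%, half the change at 50 days. Assumed: g as above; central volume V1; inter-compartmental clearance solved so that the initial half-life is 12 days; bolus in place of the 30–60 minute infusion; eventual steady state read at 60 cycles.

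| Model | Cycle 3/Cycle 1 trough ratio | Eventual ratio | Cycle 3 trough, % of eventual | C4 CEOI, % of eventual |
|---|---|---|---|---|
| One-compartment, half-life 12 to 14 days | 1.50–1.53 | 1.77–1.84 | 83–85% | 94–95% |
| Two-compartment, CL −20%, V1 3.5–5 L | about 1.6 | about 2.0–2.2 | 76–79% | 97–98% |
| One-compartment, CL −28% | 1.62–1.69 | 2.23–2.41 | 70–73% | 87–89% |
| Two-compartment, CL −28%, V1 3–8 L | 1.63–1.78 | 2.33–2.64 | 67–71% | 93–98% |

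The 20% row is there because, in the two-compartment model, a full 28% fall gives a late half-life of 14.7–15.2 days, whereas a 20% fall gives the stated 14. The one-compartment rows keep the stated half-life but not the stated clearance: ln 2/12 × 11 = 0.64 L/day, not 0.92. No row satisfies every reported figure.

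**4. Later troughs the plan already samples.** Across the one-compartment and 28% rows, the ratios to Cycle 1 are 1.61–2.39 at Cycle 5 (pre-dose C6D1), 1.67–2.61 at Cycle 8 (pre-dose C9D1) and 1.70–2.63 at Cycle 11 (pre-dose C12D1). Measured against Cycle 11 rather than the distant limit, the Cycle 3 trough is still only 67.5–88.5%.

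**5. The Cycle 4 trough.** SAP Table 2 defines a cycle's trough as the concentration before the next dose. A Cycle 4 trough is therefore pre-dose C5D1. The schedule (SAP Appendix 2, note 19) takes pre-dose samples at C2D1, C4D1, C6D1, C9D1 and C12D1, but none at C5D1. The equation in 10.3.1.2 needs pre-dose C4D1 and C2D1, and both are scheduled.

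**The case against.** The best case for the plan has five parts.

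- **The ratio is correct as defined.** It is an observed Cycle 3/Cycle 1 quantity. A reader might infer that the plan understates accumulation; it does so only if the number is taken as a steady-state value. This stands, although the sentence invites that reading.
- **The larger figures sit badly with the protocol.** Eventual trough ratios of 2.2–2.6 are above the reported less-than-twofold accumulation, and the two-compartment models with a 28% fall overshoot the 14-day late half-life. This is not decisive, because the measure behind the twofold figure is not stated, but it favours the milder rows. The SAP also cites previous studies that cannot be seen here. Even so, no falling-clearance model that was run brings the Cycle 3 trough above 85%.
- **Later exposure is already reported.** SAP 10.1.1 derives CEOI and trough at other cycles, 10.3 summarises by cycle, and exposure-response has a separate plan (SAP 11.1). A continuing rise in trough would be visible. This stands and limits the consequence.
- **The Cycle 4 wording is resolved nearby.** The second paragraph and equation of 10.3.1.2 make the intent clear. A reader might infer that the slip itself causes understatement, or that a programmer would divide by a zero pre-dose Cycle 1 value. Neither is supported: Table 2 makes the Cycle 1 trough pre-dose C2D1. The contradiction remains in the instruction addressed to the programmer.
- **Later ratios may be sparse.** Each cohort has up to six evaluable participants. Protocol 2.3.2 reports AE-related delays in 51% and reductions in 32% at 2.5 mg/kg in earlier studies. This is fair, so later ratios should be conditional on data.

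**Conclusion.** The steady-state sentence does not fit the protocol's description of ADC clearance. The ADC Cycle 3 trough is roughly 67–85% of its eventual level, against the 97.4% implied by constant clearance. The range rests on assumed shape, central volume and inter-compartmental clearance; the milder end fits the 14-day late half-life and the less-than-twofold accumulation better.

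The point is limited to ADC trough. Ro(CEOI) is about 96–98% of its eventual value in the two-compartment model with V1 of 3.5–5 L. It is lower in the one-compartment variants, which have no distribution phase. The documents give no time-varying clearance for total antibody or cys-mcMMAF, so extending the finding to them is not supported.

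The Cycle 4 trough wording is a separate internal contradiction. Severity is minor: this is a descriptive secondary PK summary, and no hypothesis, sample size or escalation rule uses the ratio.

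**What to change.** - Delete the steady-state sentence in SAP 10.3.1.2, or qualify it by reference to the falling ADC clearance in Protocol 2.3.3.
- Label the outputs as observed Cycle 3 accumulation (trough) and observed Cycle 4 accumulation (CEOI).
- In the first paragraph of 10.3.1.2 and in 14.5.3, replace the Cycle 4 trough with Cycle 3 Ctrough (pre-dose C4D1) over Cycle 1 Ctrough (pre-dose C2D1).
- Where data permit, add trough ratios from the pre-dose C6D1, C9D1 and C12D1 samples, with the number of contributing participants and a note that few will meet the no-delay, same-dose condition.

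The cost is SAP wording and a few derived rows. No new samples or visits are needed.

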- 17. Echocardiography for LVEF performed within 3 months of screening are acceptable as screening value. For participants with an abnormal LVEF (per institutional standards), the participant is to follow-up with a cardiologist.
- 18. ECGs on dosing days: Triplicate ECGs to be performed at pre-dose (within 30 minutes prior to SOI) and EOI at cycle 1. Triplicate ECGs should be collected prior to PK sample on Cycle 1 Day 2, Day 4, Day 8 and Cycle 1 Day 15. Single ECG at screening, at all other cycles, and End of Study Treatment. On days where ECG time points align with PK sampling time points, ECGs must be performed within 30 minutes prior to PK samples being drawn (PK sample must be taken at the exact nominal time). ECGs will be collected and stored at site. See SRM for details on collection regarding ECGs.
- 19. PK samples to be taken in all participants for belantamab mafodotin ADC, total antibody and cys-mcMMAF measurements on:
 - C1D1 at pre-dose (within 30 minutes prior to SOI), at the end of infusion (EOI) (+5 min), 2 h post-SOI (±15 min), 4 h post-SOI (±15 min), 8 h post-SOI (±1 h), 24 h post-SOI (±2 h);
 - C1D4 anytime (±1 day);
 - C1D8 anytime (±1 day);
 - C1D15 anytime (±1 day);
 - C1D22 anytime (±1 day) (collect one PK sample only if the dose for the next cycle is delayed; this sample will combined)
 - For C2D1, C4D1, C6D1, C9D1, and C12D1, collect samples at pre-dose (within 30 min prior to SOI) and at the EOI (+5 min);
 - For every six cycles after C12 (e.g., C18, C24, etc.), collect one sample at pre-dose (within 30 min prior to SOI). However, one year after the first dose of last subject, PK samples will only be collected for the interpretation of ADA results in the following visits.
- 20. Collect 1 PK sample at each participant's final visit.
- 21. All ADA samples will be collected prior to each infusion at C1, C2, C4, C6, C9, C12, and every 6 cycles thereafter (C18, C24, etc.) until end of treatment (dosing days only) and at the last visit.
- 22. Disease Response Assessment: Response assessment must be conducted Q3W based on standard disease laboratory tests (serum and urine M protein test, FLC, IgD/E, if applicable), Ca corrected for albumin, bone marrow aspirate (in case of CR, or suspected PD if not evident otherwise). Assessment based on imaging has to be included in

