ocular AEs were keratopathy (71%, changes in corneal epithelium identified on eye exam, with or without symptoms), blurred vision (22%), and dry eye (13%). Decreased vision defined as Snellen score worse than 20/50 in the better seeing eye was reported in 18% of participants receiving belantamab mafodotin 2.5 mg/kg. Severe vision loss defined as 20/200 or worse in the better seeing eye was reported in 1% of participants receiving belantamab mafodotin 2.5 mg/kg.

The median time to onset of Grade 2 or above corneal findings (best corrected visual acuity or corneal examination) was 36 days (range: 19 to 143 days) in participants receiving belantamab mafodotin 2.5 mg/kg. The median time to resolution of these corneal findings was 91 days (range: 21 to 201 days).

Participants with history of dry eye were more prone to develop corneal examination findings. Therefore, active management of dry eye symptoms prior to and during treatment is recommended (*i.e.* administration of preservative-free artificial tears).

The ocular sub-study of DREAMM-2 provided no evidence that corticosteroid eye drops are beneficial in preventing or mitigating corneal events.

Infusion-related reactions

Infusion-related reactions (IRRs) are expected for biologic agents. In DREAMM-2 (data as of 31 Jan 2020), IRRs occurred in 21% of participants in the belantamab mafodotin 2.5 mg/kg, which were Grade 1 - 3 in severity. Most IRRs occurred with the first infusion and few participants experienced IRRs with subsequent infusions.

Although not protocol-mandated, pre-medications for IRR prophylaxis (including paracetamol, antihistamines, and steroids) were administered to 26%–27% of participants. One participant (2.5 mg/kg cohort) discontinued treatment due to IRRs (Grade 3 IRRs at first and second infusion).

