6.6. Dose Modification

Table 4 details the permitted dose modifications of belantamab mafodotin. Table 5 and Table 6 contain dose modification guidance for drug-related AEs. See Table 7 for dose modification guidelines for belantamab mafodotin treatment-related changes in vision.

Table 4 Permitted Dose Reductions

Starting dose	Dose reduction
2.5 mg/kg	1.9 mg/kg
3.4 mg/kg	2.5 mg/kg, 1.9 mg/kg

If the participant cannot tolerate the drug after the allowed dose reduction of belantamab mafodotin to the lowest allowed dose of 1.9 mg/kg, he or she must discontinue treatment for lack of tolerability.

In case of full resolution of symptoms which lead to dose reduction, further treatment at the previous dose level may be considered by the investigator.

If a dose is delayed, the participant should wait for the next scheduled dose to resume treatment. In individual cases where in the judgment of the Investigator waiting a full cycle to resume treatment after delay (skipping dose) related to toxicity which has resolved would be detrimental to the participant's health, the PI should contact the Medical Monitor to discuss an earlier re-start. An earlier re-start may be considered only for participants who have recovered from toxicity to at least ≤Grade 1. The dosing with belantamab mafodotin cannot occur more frequently than every 21 days (±3-day

window). In such cases, efficacy and safety assessments must remain every 3 weeks in line with initial efficacy and safety assessments on study, which may result in 2 separate visits (1 for dosing, 1 for disease assessments). Evaluations associated with a dose would be entered into the eCRF under the next scheduled cycle.

Resuming treatment with belantamab mafodotin will be possible with or without dose reduction after the toxicity has resolved to Grade 1 or less.

Table 5 Dose Modification Guidelines for Belantamab Mafodotin-Related Adverse Events

Toxicity	Grade/description of toxicity	Recommendations for Belantamab Mafodotin
Elevated serum creatinine which cannot be explained by concomitant sepsis, TLS, other severe condition with fever, or dehydration	If absolute serum creatinine increases from baseline by >0.5 mg/dL	 Repeat serum creatinine within 48 hours If confirmed: withhold therapy, institute treatment and monitoring as clinically indicated, and follow for resolution Discuss any further dosing with Medical Monitora

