10.1.1. Non-compartmental Analysis

- Pharmacokinetic parameters described in [Table 2](#) below, will be determined separately for each analyte, as data permit.
- The pharmacokinetic parameters under protocol amendment 3 or later will be calculated by standard non-compartmental analysis according to current working practices and using Phoenix WinNonlin, version 6.3 or later, as data permit.
- The pharmacokinetic parameters CEOI and Ctrough will be determined directly from the concentration-time dataset for the other cycles under protocol amendment 3 and for participants enrolled prior to protocol amendment 3, as data permit.

Note: For the dosing occasions with only predose and end of infusion samples, the end of infusion concentration (CEOI) will not be identified as Cmax.

- All calculations of non-compartmental parameters will be based on actual sampling times.

Table 2 Derived Pharmacokinetic Parameters

Parameter	Parameter Description
AUC(0-t)	Area under the concentration-time curve from time zero to the time of the last quantifiable concentration (C(t)) will be calculated using the linear trapezoidal rule for each incremental trapezoid and the log trapezoidal rule for each decremental trapezoid
AUC(0- τ)	Area under the concentration-time curve during the dosing interval ($\tau=504h$, this parameter will be calculated only for ADC and total antibody)
AUC(0-168)	Area under the concentration-time curve from time 0 to 168h (This parameter will be calculated only for cys-mcMMAF)
AUC(0- ∞)	Area under the concentration-time curve extrapolated to infinity will be calculated as: $AUC = AUC(0-t) + C(t) / \lambda_z$
%AUCex	The percentage of AUC (0- ∞) obtained by extrapolation (%AUCex) will be calculated as: $[\text{AUC}(0-\infty) - \text{AUC}(0-t)] / \text{AUC}(0-\infty) \times 100$
Cmax	Maximum observed concentration, determined directly from the concentration-time data for each cycle. Cmax will not be derived when only predose and EOI samples were collected.
tmax	Time to reach Cmax, determined directly from the concentration-time data for each cycle

Parameter	Parameter Description
C_τ , C_{trough}	Trough concentration prior to the next dose for each cycle
CEOI	Observed plasma concentration at the end of infusion
$t_{1/2}$	Apparent terminal half-life will be calculated as: $t_{1/2} = \ln(2) / \lambda_z$
t_{last}	Time of last observed quantifiable concentration
CL	Clearance (This parameter will be calculated only for ADC and total antibody)

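### The no-delay condition for Ro(Ctrough) stops at dose 3, but the date of dose 4 fixes when the Cycle 3 trough is drawn, so a late dose 4 biases the ratio downward

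*SAP*

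**What the plan says.** SAP 10.3.1.2 defines two accumulation ratios. Ro(CEOI) divides the end-of-infusion concentration at C4D1 by that at C1D1. Ro(Ctrough) divides the Cycle 3 trough by the Cycle 1 trough, and the numerator is specified as "Ctrough at Cycle 3 (predose at C4D1) for Ro(Ctrough").

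The eligibility conditions differ. For the trough ratio: "Participants must receive the same dose without delay or change for the first three cycles to derive Ro(Ctrough"). For the other ratio the condition runs "for the first four cycles to derive Ro(CEOI) (i.e., with dosing delays of ≤ 3 days").

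The following passages decide when the numerator is measured:

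- SAP 10.1.1, Table 2, defines Ctrough as "Trough concentration prior to the next dose for each cycle". It sets no limit on the time since the previous dose.
- Protocol 1.3, footnote 19: "For C2D1, C4D1, C6D1, C9D1, and C12D1, collect samples at pre-dose (within 30 min prior to SOI"). The C4D1 sample is therefore tied to the start of the dose 4 infusion.
- Protocol 6.6: "If a dose is delayed, the participant should wait for the next scheduled dose to resume treatment". An earlier re-start is possible in individual cases.
- SAP 6.5 counts a delay against the dose that is late, measured from the previous actual dose date plus 21 days.

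**The concern.** The delay that moves the numerator is the delay of dose 4, and the condition does not cover it. As written, the rule excludes a participant whose dose 2 or dose 3 was 4 days late. It keeps one whose first three doses were on time and whose dose 4 was postponed by weeks. For that participant the Cycle 3 trough has had extra time to decay, but it is divided by a Cycle 1 trough taken at about 21 days. The SAP's own premise is steady state for a third dose given at the planned interval, and a late sample does not meet it.

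No other rule closes the gap. Ctrough is read directly as an observed concentration, so the use of actual sampling times does not correct it. SAP 14.5.2 has the impact of major timing deviations assessed only as appropriate, which is discretionary. The back-up sample for a late next dose (C1D22) exists for Cycle 1 only, so it protects the denominator but not the numerator.

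What is at stake is the trough accumulation result, which Tables 6.023 to 6.025 report with 95% confidence intervals in cohorts of up to six. Lateness can only lower a trough, so the errors do not average out.

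**Working it through.** **Which doses the condition covers.** CEOI at C4D1 depends on doses 1 to 4, and its condition is four cycles. In this section, then, N cycles means N doses. If it meant N completed 21-day intervals, the CEOI rule would require an on-time dose 5, which cannot affect a concentration at dose 4. SAP 6.5 agrees: a late dose 4 is a delay of dose 4. Three cycles therefore means doses 1 to 3.

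**Inputs (Protocol 2.3.3, ADC).** The half-life is 12 days at Cycle 1 and 14 days later, accumulation is less than 2-fold, and the dosing interval is 21 days.

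**Formulas (mono-exponential superposition).** Let r = 2^(−21/t½).

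- Dose 4 on time: Ro = 1 + r + r².
- Dose 4 late by d days: Ro = (1 + r + r²) × 2^(−d/t½).
- Ratio at full steady state: 1/(1 − r).

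**Check against the plan's own statements.**

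- t½ = 12: r = 0.297, Ro = 1.386, steady state 1.423, and 1.386/1.423 = 97%.
- t½ = 14: r = 0.354, Ro = 1.479, steady state 1.547, and 1.479/1.547 = 96%.

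Both ratios are below 2, as Protocol 2.3.3 reports. Both are near steady state by the third trough, as SAP 10.3.1.2 assumes.

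**Effect of a late dose 4 on one participant's ratio.**

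| Dose 4 late by | t½ = 12 | t½ = 14 |
|---|---|---|
| 0 days | 1.386 | 1.479 |
| 3 days | 1.165 | 1.274 |
| 7 days | 0.925 | 1.045 |
| 14 days | 0.617 | 0.739 |
| 21 days | 0.412 | 0.523 |

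At 21 days late the factor is 2^(−21/12) = 0.297 or 2^(−21/14) = 0.354. The individual ratio falls below 1 once d exceeds t½ × log2(1 + r + r²), which is 5.65 or 7.90 days.

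**Effect on the geometric mean of six ratios.** If m participants are 21 days late, the factor is 2^(−21m/(6·t½)).

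- m = 1: 1.386 × 0.817 = 1.13, or 1.479 × 0.841 = 1.24.
- m = 2 (the same factor as one in three): 1.386 × 0.667 = 0.92, or 1.479 × 0.707 = 1.05.

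**Sensitivity to falling clearance.** A two-compartment model was run with clearance 0.92 L/day falling by 28%, half of the fall by day 50, and Vss 11 L. It needs two assumptions that the documents do not give: a central volume of 3 to 6 L and a sigmoid exponent of 3. The ADC ratio is then 1.74 to 1.77 on time, about 1.24 to 1.25 at 7 days late and about 0.63 to 0.64 at 21 days late. It crosses 1 at about 11.5 days. The direction is the same, and the individual ratio is still far below its on-time value at 21 days.

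**The case against.** The strongest objection is that the 42-day trough may never arise. Protocol 6.6 describes the default wait as skipping a dose, and footnote 9 of the schedule provides for visits without dosing. If the skipped dose uses up Cycle 4, the next dose is Cycle 5, for which no PK sample is scheduled. The ratio is then missing, not biased. The documents do not settle the numbering. Footnote 19 speaks of the next cycle's dose being delayed, and SAP 6.5 has delay categories of 22-42 and more than 42 days for a single dose, both of which suggest that the cycle label moves with the dose. So the objection limits the 21-day case without removing it. It does not touch shorter delays after an earlier re-start.

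A reader might infer that a late dose 4 is likely. The documents do not support that. The 51% with AE-driven delays at 2.5 mg/kg (Protocol 2.3.2) is for any time on treatment, pooled over two studies. Median onset of Grade 2 or above corneal findings "was 36 days (range: 19 to 143 days) in participants receiving belantamab mafodotin 2.5 mg/kg", which falls before dose 3 is due on Day 43. A delay at dose 3 is already excluded. Such a finding also need not lead to a hold, because one tier of Table 7 is a dose reduction with treatment continued.

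The consequence is also modest. The analysis is descriptive, Ro is not among the parameters listed in Protocol 9.4.10, and no decision rule uses it. Individual ratios and dose delays are both listed, so an alert reader of the listings could find an affected value. That is a reason to rank the point below a primary-endpoint error, but not to leave the rule as it is.

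**Conclusion.** The concern holds. As written, SAP 10.3.1.2 can admit a Cycle 3 trough drawn more than 24 days after dose 3, and every such value pulls Ro(Ctrough) down. For the ADC the individual ratio drops from 1.39-1.48 to 0.41-0.52 if dose 4 is 21 days late and keeps the Cycle 4 label.

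It would go too far to say that the reported summary will show decline. With one such participant in six, the geometric mean understates accumulation but stays at 1.13 to 1.24. It would take about two in six, or one in three, to bring it near 1. The same sizes cannot be carried over to total antibody or cys-mcMMAF, because the documents give no half-life for either; only the direction carries over.

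The sizes rest on mono-exponential decline with the protocol's half-life, and on the dose-based reading of the three-cycle condition. If the sponsor meant three completed intervals, the same sentence is still needed to say so.

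**What to change.** In SAP 10.3.1.2, keep the condition on doses 1 to 3 and add one sentence for Ro(Ctrough): the C4D1 pre-dose sample is used only if dose 4 was given no more than 3 days late, that is, the sample was taken no more than 24 days after dose 3. Otherwise the Cycle 3 trough is set to missing for this ratio. A dose change at dose 4 need not exclude the participant, since it cannot affect a sample taken before that dose.

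Also align the wording. The opening sentence of 10.3.1.2 and the programmer's derivation in 14.5.3 refer to the trough at Cycle 4, while the formula uses the Cycle 3 trough.

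The cost is one sentence and one date check in the program. It is an analysis eligibility rule and changes no dosing or clinical instruction. The downside is possibly fewer evaluable ratios in a cohort of up to six. At the 3-day limit the ADC ratio is still 1.17 to 1.27 under the mono-exponential model, so the tolerance already used in this section is adequate.
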